7.2.2 Definition of an Overdose for This Protocol

For purposes of this trial, an overdose of pembrolizumab will be defined as any dose of 1,000 mg or greater (\geq 5 times the indicated dose). No specific information is available on the treatment of overdose of pembrolizumab. Appropriate supportive treatment should be provided if clinically indicated. In the event of overdose, the subject should be observed closely for signs of toxicity. Appropriate supportive treatment should be provided if clinically indicated.

If an adverse event(s) is associated with ("results from") the overdose of a Merck product, the adverse event(s) is reported as a serious adverse event, even if no other seriousness criteria are met.

If a dose of Merck's product meeting the protocol definition of overdose is taken without any associated clinical symptoms or abnormal laboratory results, the overdose is reported as a non-serious Event of Clinical Interest (ECI), using the terminology "accidental or intentional overdose without adverse effect."

7.2.3 Events of Clinical Interest

Selected non-serious and serious adverse events are also known as Events of Clinical Interest (ECI) and must be recorded in the trial database. Events of clinical interest for this trial include:

- 1. an overdose of Merck product, as defined in "Definition of an Overdose for This Protocol" that is not associated with clinical symptoms or abnormal laboratory results.
- 2. an elevated AST or ALT lab value that is greater than or equal to 3X the upper limit of normal and an elevated total bilirubin lab value that is greater than or equal to 2X the upper limit of normal and, at the same time, an alkaline phosphatase lab value that is less than 2X the upper limit of normal, as determined by way of protocol-specified laboratory testing or unscheduled laboratory testing.*

*Note: These criteria are based upon available regulatory guidance documents. The purpose of the criteria is to specify a threshold of abnormal hepatic tests that may require an additional evaluation for an underlying etiology. The trial site guidance for assessment and follow up of these criteria can be found in the Investigator Trial File Binder (or equivalent).

1. Additional adverse events:

A separate guidance document has been provided entitled "Event of Clinical Interest Guidance Document" (previously entitled, "Event of Clinical Interest and Immune-Related Adverse Event Guidance Document"). This document can be found in the Appendix and provides guidance regarding identification, evaluation and management of ECIs and irAEs.

Subjects should be assessed for possible ECIs prior to each dose. Lab results should be evaluated and subjects should be asked for signs and symptoms suggestive of an immune-related event. Subjects who develop an ECI thought to be immune-related should have additional testing to rule out other etiologic causes. If lab results or symptoms indicate a possible immune-related ECI, then additional testing should be performed to rule out other etiologic causes. If no other cause is found, then it is assumed to be immune-related.

7.2.4 Evaluating Adverse Events

An investigator who is a qualified physician will evaluate all adverse events according to the NCI Common Terminology for Adverse Events (CTCAE), version 4.0. Any adverse event

which changes CTCAE grade over the course of a given episode will have each change of grade recorded on the adverse event. PDMS/CORe will be the electronic database used for this study.

All adverse events regardless of CTCAE grade must also be evaluated for seriousness.

7.3 Investigator Communications with Merck

All reports of overdose with and without an adverse event must be reported within 24 hours to the IND Office and within 2 working days hours to Merck Global Safety. (Attn: Worldwide Product Safety; [contact])

Although pregnancy and lactation are not considered adverse events, it is the responsibility of investigators or their designees to report any pregnancy or lactation in a subject (spontaneously reported to them), including the pregnancy of a male subject's female partner that occurs during treatment with pembrolizumab on the trial or within 120 days of completing pembrolizumb treatment on the trial, or 30 days following cessation of pembrolizumab treatment if the subject initiates new anticancer therapy, whichever is earlier. All subjects and female partners of male subjects who become pregnant must be followed to the completion/termination of the pregnancy. The outcome of the pregnancy will be reported to the IND Office and to Merck Global Safety (Attn: Worldwide Product Safety; [contact]) without delay, and within 24 hours to the IND Office and within 2 working days to Merck. If the outcome is a serious adverse experience (e.g., death, abortion, congenital anomaly, or other disabling or life-threatening complication to the mother or newborn),

it must be reported as serious events (Important Medical Events). If the pregnancy continues to term, the outcome (health of infant) must also be reported.

7.3.1. Immediate Reporting Serious Adverse Events to Merck

A serious adverse event is any adverse event occurring at any dose or during any use of Merck's product that:

- Results in death;
- Is life threatening;
- Results in persistent or significant disability/incapacity;
- Results in or prolongs an existing inpatient hospitalization;
- Is a congenital anomaly/birth defect;
- Is a new cancer (that is not a condition of the study);
- Is associated with an overdose;
- Is another important medical event

Refer to Table 6 for additional details regarding each of the above criteria.

Any serious adverse event, or follow up to a serious adverse event, including death due to any cause other than progression of the cancer under study that occurs to any subject from the time the subject is randomized through 90 days following cessation of treatment, or the initiation of new anti-cancer therapy, whichever is earlier, whether or not related to Merck product, must be reported within 5 working days of knowledge of the event to the IND Office and within 2 working days to Merck Global Safety.

ECIs (both non-serious and serious adverse events) identified in this guidance document from the date of first dose through 90 days following cessation of treatment, or 30 days after the initiation of a new anticancer therapy, whichever is earlier, need to be reported within 24 hours to the IND Office and within 2 working days to Merck Global Safety(Attn: Worldwide Product Safety; [contact]), regardless of attribution to study treatment, consistent with standard SAE reporting guidelines.

Non-serious Events of Clinical Interest will be forwarded to Merck Global Safety and will be handled in the same manner as SAEs.

Additionally, any serious adverse event, considered by an investigator who is a qualified physician to be related to Merck product that is brought to the attention of the investigator at any time outside of the time period specified in the previous paragraph also must be reported immediately to the IND Office and to Merck.

All subjects with serious adverse events must be followed up for outcome.

Product: MK-3475

Protocol/Amendment No.:

Table 6 Evaluating Adverse Events

An investigator who is a qualified physician, will evaluate all adverse events as to:

V4.0 CTCAE Grading	Grade 1	Mild; asymptomatic or mid symptoms; clinical or diagnostic observations only; intervention not indicated.		
	Grade 2	Moderate; minimal, local or noninvasive intervention indicated; limiting age-appropriate instrumental ADL.		
	Grade 3	Severe or medically significant but not immediately life-threatening; hospitalization or prolongation or hospitalization indicated;		
		disabling; limiting self-care ADL.		
	Grade 4	Life threatening consequences; urgent intervention indicated.		
	Grade 5	Death related to AE		
Seriousness	A serious adverse event is any adverse event occurring at any dose or during any use of Merck product that:			
1	†Results in death; or			
	†Is life threatening; or places the subject, in the view of the investigator, at immediate risk of death from the event as it occurred (Note: This does not include an			
	adverse event that, had it occurred in a more severe form, might have caused death.); or			
	†Results in a persistent or significant disability/incapacity (substantial disruption of one's ability to conduct normal life functions); or			
	†Results in or prolongs an existing inpatient hospitalization (hospitalization is defined as an inpatient admission, regardless of length of stay, even if the			
	hospitalization is a precautionary measure for continued observation. (Note: Hospitalization [including hospitalization for an elective procedure] for a preexisting			
	condition which has not worsened does not constitute a serious adverse event.); or			
	†Is a congenital anomaly/birth defect (in offspring of subject taking the product regardless of time to diagnosis);or			
	Is a new cancer; (that is not oral cancer) or			
	Is an overdose (whether accidental or intentional). Any adverse event associated with an overdose is considered a serious adverse event. An overdose that is not			
	associated with an adverse event is considered a non-serious event of clinical interest and must be reported within 24 hours.			
	Other important medical events that may not result in death, not be life threatening, or not require hospitalization may be considered a serious adverse event when,			
	based upon appropriate medical judgment, the event may jeopardize the subject and may require medical or surgical intervention to prevent one of the outcomes			
	listed previously (designated above by a †).			
Duration	Record the start and stop dates of the adverse event. If less than 1 day, indicate the appropriate length of time and units			
Action taken	Did the adverse event cause the Merck product to be discontinued?			
Relationship to	Did the Merck product cause the adverse event? The determination of the likelihood that the Merck product caused the adverse event will be provided by an			
test drug	investigator who is a qualified physician. The investigator's signed/dated initials on the source document or worksheet that supports the causality noted on the AE			
	form, ensures that a medically qualified assessment of causality was done. This initialed document must be retained for the required regulatory time frame. The criteria below are intended as reference guidelines to assist the investigator in assessing the likelihood of a relationship between the test drug and the adverse event			
	based upon the available information.			
	The following components are to be used to assess the relationship between the Merck product and the AE; the greater the correlation with the components and			
	their respective elements (in number and/or intensity), the more likely the Merck product caused the adverse event (AE):			
	Exposure	Is there evidence that the subject was actually exposed to the Merck product such as: reliable history, acceptable compliance assessment (pill		
	Exposure	count, diary, etc.), expected pharmacologic effect, or measurement of drug/metabolite in bodily specimen?		
	Time Course	Did the AE follow in a reasonable temporal sequence from administration of the Merck product?		
		Is the time of onset of the AE compatible with a drug-induced effect (applies to trials with investigational medicinal product)?		
	Likely Cause	Is the AE not reasonably explained by another etiology such as underlying disease, other drug(s)/vaccine(s), or other host or environmental factors		

Product: MK-3475

Protocol/Amendment No.:

The following com Dechallenge Rechallenge	Was the Merck product discontinued or dose/exposure/frequency reduced? If yes, did the AE resolve or improve? If yes, this is a positive dechallenge. If no, this is a negative dechallenge. (Note: This criterion is not applicable if: (1) the AE resulted in death or permanent disability; (2) the AE resolved/improved despite continuation of the Merck product; or (3) the trial is a single-dose drug trial); or (4) Merck product(s) is/are only used one time.) Was the subject re-exposed to the Merck product in this study? If yes, did the AE recur or worsen? If yes, this is a positive rechallenge. If no, this is a negative rechallenge. (Note: This criterion is not applicable if: (1) the initial AE resulted in death or permanent disability, or (2) the trial is a single-dose drug trial); or (3) Merck product(s) is/are used only one time).
ğ	If yes, did the AE resolve or improve? If yes, this is a positive dechallenge. If no, this is a negative dechallenge. (Note: This criterion is not applicable if: (1) the AE resulted in death or permanent disability; (2) the AE resolved/improved despite continuation of the Merck product; or (3) the trial is a single-dose drug trial); or (4) Merck product(s) is/are only used one time.) Was the subject re-exposed to the Merck product in this study? If yes, did the AE recur or worsen? If yes, this is a positive rechallenge. If no, this is a negative rechallenge. (Note: This criterion is not applicable if: (1) the initial AE resulted in death or permanent disability, or (2) the trial is a single-dose drug trial); or
Rechallenge	If yes, this is a positive dechallenge. If no, this is a negative dechallenge. (Note: This criterion is not applicable if: (1) the AE resulted in death or permanent disability; (2) the AE resolved/improved despite continuation of the Merck product; or (3) the trial is a single-dose drug trial); or (4) Merck product(s) is/are only used one time.) Was the subject re-exposed to the Merck product in this study? If yes, did the AE recur or worsen? If yes, this is a positive rechallenge. If no, this is a negative rechallenge. (Note: This criterion is not applicable if: (1) the initial AE resulted in death or permanent disability, or (2) the trial is a single-dose drug trial); or
Rechallenge	(Note: This criterion is not applicable if: (1) the AE resulted in death or permanent disability; (2) the AE resolved/improved despite continuation of the Merck product; or (3) the trial is a single-dose drug trial); or (4) Merck product(s) is/are only used one time.) Was the subject re-exposed to the Merck product in this study? If yes, did the AE recur or worsen? If yes, this is a positive rechallenge. If no, this is a negative rechallenge. (Note: This criterion is not applicable if: (1) the initial AE resulted in death or permanent disability, or (2) the trial is a single-dose drug trial); or
Rechallenge	of the Merck product; or (3) the trial is a single-dose drug trial); or (4) Merck product(s) is/are only used one time.) Was the subject re-exposed to the Merck product in this study? If yes, did the AE recur or worsen? If yes, this is a positive rechallenge. If no, this is a negative rechallenge. (Note: This criterion is not applicable if: (1) the initial AE resulted in death or permanent disability, or (2) the trial is a single-dose drug trial); or
Rechallenge	Was the subject re-exposed to the Merck product in this study? If yes, did the AE recur or worsen? If yes, this is a positive rechallenge. If no, this is a negative rechallenge. (Note: This criterion is not applicable if: (1) the initial AE resulted in death or permanent disability, or (2) the trial is a single-dose drug trial); or
Rechallenge	If yes, did the AE recur or worsen? If yes, this is a positive rechallenge. If no, this is a negative rechallenge. (Note: This criterion is not applicable if: (1) the initial AE resulted in death or permanent disability, or (2) the trial is a single-dose drug trial); or
	If yes, this is a positive rechallenge. If no, this is a negative rechallenge. (Note: This criterion is not applicable if: (1) the initial AE resulted in death or permanent disability, or (2) the trial is a single-dose drug trial); or
	(Note: This criterion is not applicable if: (1) the initial AE resulted in death or permanent disability, or (2) the trial is a single-dose drug trial); or
	(3) Merck product(s) is/are used only one time).
	NOTE: IF A RECHALLENGE IS PLANNED FOR AN ADVERSE EVENT WHICH WAS SERIOUS AND WHICH MAY HAVE BEEN
	CAUSED BY THE MERCK PRODUCT, OR IF REEXPOSURE TO THE MERCK PRODUCT POSES ADDITIONAL POTENTIAL
	SIGNIFICANT RISK TO THE SUBJECT, THEN THE RECHALLENGE MUST BE APPROVED IN ADVANCE BY THE Principle
	Investigator AS PER DOSE MODIFICATION GUIDELINES IN THE PROTOCOL.
Consistency	Is the clinical/pathological presentation of the AE consistent with previous knowledge regarding the Merck product or drug class pharmacology
	or toxicology?
relationship will be g consideration of the	e reported on the ease report forms /worksheets trial database by an investigator who is a qualified physician according to his/her best clinical above elements.
following	Use the following scale of criteria as guidance (not all criteria must be present to be indicative of a Merck product relationship).
sonable	There is evidence of exposure to the Merck product. The temporal sequence of the AE onset relative to the administration of the Merck product
ek product	is reasonable. The AE is more likely explained by the Merck product than by another cause.
reasonable product	Subject did not receive the Merck product OR temporal sequence of the AE onset relative to administration of the Merck product is not reasonable OR there is another obvious cause of the AE. (Also entered for a subject with overdose without an associated AE.)
1	with Trial Treatment Profile relationship will be consideration of th following onable k product

Proprietary Information of MD Anderson Document Product: JMK 2475, 2016 NCT02882282

8.1 STATISTICAL CONSIDERATIONS

8.2 Study design and sample size justifications

This randomized phase 2 trial focuses on the definitive primary endpoint of oral cancer-free survival, thus eliminating the limitations of utilizing intermediate endpoints for efficacy analysis. Unfortunately, clinical and/or histologic responses of IEN lesions to chemoprevention interventions only marginally correlate with long-term oral cancer-free survival, as demonstrated by larger-scale retinoid-based therapy trials. As such, the most appropriate way to accurately estimate activity of a candidate drug to manage oral IEN is to use oral cancer-free survival as an endpoint.

The advantages of selecting a molecularly-defined high risk group as the eligible population include: (1) increased number of expected events, thus reducing the sample size; (2) avoidance of exposure of low-risk individuals to the drug, who are unlikely to develop oral cancer and therefore, unlikely to benefit from prevention interventions; (3) improvement of benefit/risk rations and benefit/cost ratios, justifying further use of the drug if positive effects are identified.

The proposed study will be an open-label, observation-controlled randomized study to evaluate the effect of pembrolizumab in a high-risk group of oral IEN patients. There will be two categories of high-risk patients in this study: (a) loss of heterozygosity (LOH) at 3p14 and/or 9p21 in the oral IEN of patients with a history of curatively treated oral cancer and (b) LOH at 3p14 and/or 9p21 plus at one other chromosomal region in the IEN of patients with no oral cancer history.

Study Duration: The trial period is 7 years with 4 years of accrual and 3 additional years of follow-up after last patient's enrollment.

Study Endpoints: The primary endpoint is oral cancer-free survival in patients receiving pembrolizumab as compared with the observation group. Multiple secondary and/or exploratory endpoints will be assessed as outlined in Section 3.2 and 3.3.

Treatment Groups: This is a 2-arm open-label Phase II single-center trial of pembrolizumab versus observation in patients with oral IEN. The trial will randomize 104 patients (1:1)to receive pembrolizumab versus observation.

Sample Size Justification

The planned sample size is 104 patients. In the recently completed EPOC study, 5.7 patients per month were screened for LOH high risk profiles, 68% were LOH positive, and 59% of the LOH positive patients agreed to be randomized. That study had similar eligibility criteria as proposed herein. As such, we anticipate that for this trial, 250 patients will be screened over 4 years to achieve a total of 104 patients randomized. Sample size calculation was made on the basis of the primary endpoint of the study, time from randomization to onset of oral cancer or death.

Proprietary Information of MD Anderson Document Product: JMK12475, 2016 NCT02882282

Details of the assumptions used for the sample size calculation are listed below.

- 1. The study has a 4-year period to accrue 56 oral IEN/prior cancer and 48 IEN-alone patients, with an additional 3 years of follow-up after last patient is enrolled. The total study duration is 7 years.
- 2. The anticipated yield of LOH screening (described earlier) will be approximately 68%. Assuming an accrual rate of 59% eligible patients, we will need to screen a total of 250 oral IEN patients in order to reach our total accrual goal.
- 3. Time-to-oral cancer development follows an exponential distribution. Based on the data described earlier, 21% of the patients with IEN/LOH associated with curatively treated oral cancer will develop oral cancer in two years, and 15% of the IEN/LOH-alone patients will develop oral cancer in two years.
- 4. Pembrolizumab, the active treatment, can reduce the 2-year oral cancer rate by 52% for the IEN/LOH-cancer history group, i.e., 2-year cancer rate will be reduced from 21% to 10%. This corresponds to a hazard ratio of 0.45. We assume the same treatment effect (hazard ratio) in the IEN/LOH-alone group, corresponding to the 2-year oral cancer rate reduction from 15% to 7%. The parameters, lambda, for the exponential distributions are 0.1179 (control) and 0.053 (treatment) in IEN/LOH-cancer history patients and 0.0813 (control) and 0.0366 (treatment) in IEN/LOH-alone patients, respectively.
- 5. We assume the rate of lost-to-follow up, which includes patient refusal, early drop out, or competing risk, etc. is 10%. The distribution of the time to loss to follow-up is assumed to be uniform.
- 6. Stratified log-rank test is used to compare the cancer-free survival between the active and control groups.
- 7. One interim analysis is planned at the end of year 3. The final analysis will be performed at the end of the study (year 7). We will apply the group sequential design with the O'Brien-Fleming boundary to control the overall one-sided type I error rate to 10%. The stopping boundaries, i.e. Standardized Z Scale, are 1.899 at the interim analysis and 1.343 at the final analysis

Based on the above assumptions, we ran simulation studies with 10,000 replications. The results show that a total of 104 patients will allow us to have 79% power with a one-sided 10% type I error rate. The study will have 88% power to detect a hazard ratio of 0.4.

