5.10 Clinical Criteria for Early Trial Termination

Early trial termination will be the result of the criteria specified below:

1. Quality or quantity of data recording is inaccurate or incomplete

- 2. Poor adherence to protocol and regulatory requirements
- 3. Incidence or severity of adverse drug reaction in this or other studies indicates a potential health hazard to subjects
- 4. Plans to modify or discontinue the development of the study drug

In the event of Merck decision to no longer supply study drug, ample notification will be provided so that appropriate adjustments to subject treatment can be made.

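### The boundaries 1.899/1.343 fit an interim at 50% information, but the year-3 look has about 26–27% under uniform accrual, so it is far less strict than O'Brien-Fleming and overall alpha is about 10.6%

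*Combined protocol and SAP*

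**What the plan says.** Section 8.2 of the combined protocol and SAP sets the calendar first: "The trial period is 7 years with 4 years of accrual and 3 additional years of follow-up after last patient's enrollment". Assumption 1 gives the composition: "The study has a 4-year period to accrue 56 oral IEN/prior cancer and 48 IEN-alone patients". Assumption 7 then says "One interim analysis is planned at the end of year 3", places the final analysis at year 7, and adds "We will apply the group sequential design with the O'Brien-Fleming boundary to control the overall one-sided type I error rate to 10" percent. The critical values are given as fixed numbers: "The stopping boundaries, i.e. Standardized Z Scale, are 1.899 at the interim analysis and 1.343 at the final analysis".

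Sections 8.2 and 8.3 give no event count for either analysis, no information fraction, no spending function, and no rule for recomputing the boundaries if the interim falls elsewhere. The shape of accrual over the 4 years is not stated. Section 5.10 opens its list of reasons for ending the trial with "Early trial termination will be the result of the criteria specified below", and none of the four entries concerns efficacy.

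**The concern.** O'Brien-Fleming critical values depend on how much of the final information is available at the interim. For a log-rank test that is, to a good approximation, the share of final events already observed. The two stated values differ by a factor of √2, which is the mark of an interim at exactly half the information. A look at year 3 of 7, with a quarter of the accrual period still to run, will come well before half the events.

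Two things are at stake. The claim that overall one-sided error is held at 10% is not exact. More importantly, the plan names a method chosen for its strictness at early looks but supplies a lenient number. An efficacy decision could be taken on very few events, in an open-label trial that is still enrolling.

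**Working it through.** **Inputs (section 8.2).**
- 56 patients with prior oral cancer and 48 without, randomized 1:1, so 28 and 24 per arm.
- Exponential hazards per year: control 0.1179 and 0.0813, treatment 0.053 and 0.0366 (hazard ratio 0.45).
- Accrual over 4 years, analyses at years 3 and 7, 10% lost uniformly in time, stratified log-rank test, one-sided alpha 0.10.
- Assumed here: uniform accrual, and loss spread uniformly over each patient's potential follow-up.

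**Step 1: reproduce the stated boundaries.** With two looks, corr(Z₁, Z₂) = √t, where t is the information fraction. Overall alpha is 1 − Φ₂(b₁, b₂; √t), with Φ₂ the bivariate normal distribution function. The classical form is b₁ = C/√t, b₂ = C. At t = 0.50 and alpha 0.10, C = 1.343 and b₁ = 1.343 × √2 = 1.899. Alpha is 0.1000, an exact match. The Lan-DeMets O'Brien-Fleming-type function at t = 0.50 gives 2.054/1.316, so the stated pair is the classical one.

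**Step 2: events at years 3 and 7.** For hazard λ, entry uniform over 4 years and no loss, the probability of an event by calendar time τ is

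(1/4) × [m − (e^(−λ(τ−m)) − e^(−λτ))/λ], with m = min(τ, 4).

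| No loss, HR 0.45 | Year 3 | Year 7 |
|---|---|---|
| Prior cancer, control (28) | 3.31 | 12.33 |
| Prior cancer, treated (28) | 1.58 | 6.48 |
| No prior cancer, control (24) | 2.03 | 7.95 |
| No prior cancer, treated (24) | 0.95 | 4.00 |
| Total | 7.9 | 30.7 |

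So t = 7.88/30.75 = 0.256. Under the null the totals are 10.7 and 40.5, so t = 0.263. With 10% loss they are 7.8 of 29.3 (t = 0.26) at HR 0.45 and 10.5 of 38.7 (t = 0.27) under the null.

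**Step 3: sensitivity of t.**

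| Variation | t |
|---|---|
| Loss 0–20%, or 10% spread over 1, 3 or 7 years | 0.256–0.275 |
| Linearly rising accrual | 0.15 |
| Linearly falling accrual | 0.35–0.36 |
| Accrual completed in 3 years | 0.32–0.33 |
| Accrual completed in 1 year | 0.46–0.48 |
| Follow-up capped at 36 months per patient | about 0.39 |

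No case reaches 0.50. Section 8.2's own rates fit roughly constant 4-year accrual: 5.7 screened per month × 0.68 × 0.59 = 2.29 randomized per month, and 104/2.29 is about 45 months.

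**Step 4: overall alpha of 1.899/1.343.**

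| t | 0.50 | 0.45 | 0.39 | 0.30 | 0.27 | 0.26 |
|---|---|---|---|---|---|---|
| alpha | 0.1000 | 0.1013 | 0.1029 | 0.1053 | 0.1061 | 0.1064 |

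A stratified log-rank simulation under the null (100,000 replicates, uniform accrual) gives 0.1065 (SE 0.0010). A single final test at 1.2816 on the same replicates gives 0.1006. So about 0.6 points come from the boundaries and little from the normal approximation. Over the accrual patterns in step 3, alpha runs from 10.1% (1-year accrual) to 10.9% (rising accrual).

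**Step 5: strictness of the interim at t = 0.27.** The interim crossing chance and power are simulated at HR 0.45 (60,000 replicates).

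| Boundaries | Interim one-sided p | Crossing at year 3 | Power |
|---|---|---|---|
| As stated, 1.899/1.343 | 0.029 | 18.9% | 78.9% |
| Classical O'Brien-Fleming, 2.50/1.297 | 0.006 | 5.7% | 79.4% |
| Lan-DeMets type, 2.96/1.284 | 0.0015 | 1.4% | 79.6% |

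Interim events at HR 0.45 have median 8 (5th to 95th percentile 4 to 12). The stated 79% power is reproduced with the year-3 look (78.9%). It is also reproduced with a look at 50% of events (78.8% in a separate 10,000-replicate run). The power figure therefore cannot show which timing the plan's simulation used.

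**The case against.** The strongest reply is that little changes. An excess of 0.6 points on a one-sided 10% test in a single-centre phase 2 trial alters no sample size and hardly any final conclusion, and power is intact. The stated pair is itself correct for equally spaced information; what is wrong is its pairing with a calendar date. All of this stands, and it limits the weight of the point.

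The figure of 26–27% rests on an accrual shape that the plan does not give. That is true, but every pattern tried stays below 50%. The 36-month participation in section 1.0, read as a cap on follow-up, narrows the gap: t is about 0.39, alpha about 10.3%, and the classical interim p about 0.017. That reading fits the plan poorly, because power would fall to about 66% against the stated 79%.

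The plan names O'Brien-Fleming, not Lan-DeMets, so the fair comparison for the interim is p = 0.029 against 0.006, and crossing 19% against 6%. The Lan-DeMets row is there because it is the proposed repair.

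A year-3 crossing is also rarely misleading if the drug works: at HR 0.45, 95% of trials that cross would also exceed 1.343 at year 7. Under the null the figure is only about 39%.

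Finally, that crossing would end the trial is an inference from the wording of assumption 7. Section 5.10 does not list efficacy.

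**Conclusion.** The concern holds. The stated boundaries are exact at 50% information. With the plan's hazards and uniform 4-year accrual, the year-3 look comes at 26–27%. Overall one-sided type I error is then about 10.6% against the stated 10%, with a range of 10.1% to 10.9% over the accrual patterns tried. Power remains about 79%.

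The error-rate excess alone would be minor. The reason to act is that the interim threshold lacks the strictness its name implies, and nothing in sections 8.2 or 8.3 corrects the boundaries to the information actually observed. This should be fixed before the interim. It does not threaten the design. The size depends on the assumed accrual shape; the direction does not.

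**What to change.** Keep the year-3 look and amend the SAP as follows.

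1. Derive both boundaries from a Lan-DeMets O'Brien-Fleming-type spending function at one-sided 0.10.
2. Take the interim fraction as observed events divided by a planned maximum fixed in the SAP, for example 30, the number expected at HR 0.45.
3. Compute the final boundary from the observed event counts so that it spends the remaining alpha.
4. Re-run the simulation, restate the operating characteristics, and state the assumed accrual pattern.
5. Say what crossing at year 3 triggers, and reconcile this with section 5.10.

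At t = 0.27 the boundaries would be 2.96/1.284. In simulation this rule gives overall alpha 10.1% (a single final test gives 10.06%) and power of about 79.6%, with a planned maximum of either 30 or 39 events.

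The work is SAP wording and one simulation run before the interim, with no change in sample size. The price is that the early look becomes nearly inert for efficacy: at HR 0.45 the chance of crossing falls from 19% to 3.3% (maximum 30) or 1.2% (maximum 39).

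There are two alternatives:
- **Keep 1.899 and raise the final boundary to about 1.385–1.387.** Simulated alpha is 10.07% and power 78.0%, about one point lower. The design should then no longer be called O'Brien-Fleming.
- **Keep 1.899/1.343 and trigger both analyses by events, at 15 and 30.** Alpha is 9.9% and power 79.4%. At HR 0.45, however, the 30th event comes at a median of 7.05 years and only 48% of trials reach it by year 7. Triggering only the interim at 15 events, with the final left at year 7, gives t = 0.39 under the null and alpha of about 10.3%, so it is not enough.
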